### 3.8.3 Vital Signs

Vital signs will be measured as indicated in the Schedule of Events in the protocol. Vital signs will include height (Screening only), weight, systolic and diastolic blood pressure (SBP and DBP), heart rate (HR), respiratory rate, and temperature (presented in Celsius).

Descriptive statistics will be provided for the values and changes from baseline for all vital signs measurements at each scheduled visit. The last, maximum, and minimum post-baseline values will also be presented. Both scheduled and unscheduled visits will be considered for summaries of the last, minimum, and maximum. Vital signs abnormalities will be evaluated using potentially clinically significant (PCS) criteria for minimum and maximum values of SBP, DBP and HR as defined in Table 3-4. The number and proportion of patients with potentially clinically significant changes in vital signs will be presented.

Vital signs assessments will also be listed by patient.

Table 3-4: Potentially clinically significant SBP, DBP and HR

Parameter	PCS criteria
Systolic blood pressure (mmHg)	Minimum SBP $\leq 90$ mmHg
	Minimum SBP decrease from baseline $> 20$ mmHg
	Maximum SBP $\geq 140$ mmHg
	Maximum SBP increase from baseline $> 20$ mmHg
Diastolic blood pressure (mmHg)	Minimum DBP $\leq 60$ mmHg
	Minimum DBP decrease from baseline $> 20$ mmHg
	Maximum DBP $\geq 100$ mmHg
	Maximum DBP increase from baseline $> 20$ mmHg
Heart rate (beats per minute)	Minimum value $\leq 60$ bpm
	Minimum HR decrease from baseline $> 20$ bpm
	Maximum value $\geq 100$ bpm
	Maximum HR increase from baseline $> 20$ bpm

Notes:

- If both the baseline and values of a parameter are beyond the same PCS limit for that parameter, then the value will be considered a PCS value only if it is more extreme (farther from the limit) than was the baseline value.
- If the baseline value for a parameter is missing and the absolute value of a parameter is beyond the PCS limit, then the value will be considered as PCS.
- If the baseline value for a parameter is missing, the change from baseline value will be missing and PCS change criteria will not be assessed.
- The missing category will count the number of patients without any values of the parameter during the period.

### 3.8.4 *Electrocardiograms*

Electrocardiograms will be performed as indicated in the Schedule of Events in the protocol. Twelve-lead ECGs will be performed locally and should be collected in triplicate, separated by approximately 5 minutes.

Continuous ECG parameters (PR, RR, QRS, QT and QTcF) will be summarized using descriptive statistics of the values and change from baseline at each scheduled visit. The last post-baseline and the maximum post-treatment values will also be presented. Both scheduled and unscheduled visits will be considered for summaries of the last and maximum post-treatment values. All triplicate ECG measurements at a particular timepoint will be averaged prior to analysis and summarization.

In addition, patients experiencing QTcF elevation or change from baseline will be tabulated by scheduled visit for the following categories:

- QTcF > 450 ms
- QTcF > 480 ms
- QTcF > 500 ms
- Increase from baseline QTcF > 30 ms
- Increase from baseline QTcF > 60 ms

ECG readings will be judged for overall clinical significance. Shift tables from baseline to the worst post-baseline result will be presented by dose cohort. Both scheduled and unscheduled visits will be used. The following categories will be used: Normal, Abnormal not clinically significant, Abnormal clinically significant.

ECG assessments will be listed by patient.

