4.4 Discontinuation of study treatment

Discontinuation of a patient from study treatment may occur or any of the following reasons:

- The patient or legal representative (such as a parent or legal guardian) withdraws consent;
- Confirmed radiographic disease progression;

Note: A patient may be granted an exception to continue on treatment with confirmed radiographic disease progression if clinically stable or clinically improved. Such cases should be discussed by the Investigator or treating physician with the Sponsor.

Note: In certain circumstances, a patient experiencing disease progression per RECIST without clinical deterioration may be allowed to continue on treatment if the Investigator considers it in the patient's best interest and in agreement between the Investigator and Sponsor. If repeated tumor assessment within 4 to 8 weeks confirms progressive disease, the patient will need to be discontinued permanently from treatment.

- Occurrence of any medical condition or circumstance that exposes the patient to substantial risk and/or does not allow the patient to adhere to the requirements of the Protocol;
- Any SAE, clinically significant AE, DLT, severe laboratory abnormality, intercurrent illness, or other medical condition which indicates to the Investigator that continued participation is not in the best interest of the patient;
- Patients who meet Hy's law will be discontinued from treatment;
- Pregnancy;
- Requirement of prohibited concomitant medication;
- Patient failure to comply with Protocol requirements or study-related procedures;
- The patient is lost to follow-up; or
- Termination of the study by the Sponsor or the regulatory authority.

Patients who discontinue for reasons noted above other than progressive disease will have post-treatment follow-up for disease status until disease progression, initiation of a non-study cancer treatment, withdrawal of consent, or lost to follow-up. In addition, each patient, irrespective of disease progression, will be followed for survival by telephone (or public records when allowed as per local regulation) until death or study termination whichever occurs first. Study staff should make every effort to complete the full panel of assessments scheduled for the End of Study Visit in addition to disease evaluation as noted above (■■■ OR ≤30 days since last

dose of study drug). The reason for patient withdrawal must be documented in the electronic case report form (eCRF).

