7.9 Electrocardiograms

Electrocardiograms will be performed as indicated in Appendix A. Twelve-lead ECGs will be performed locally and should be collected in triplicate, separated by approximately 5 minutes. When ECG measurements coincide with blood sample draws for PK, PD, or ADA sampling, the ECG measurement should be timed sufficiently prior to blood sample collection without impacting the sample collection time. Additional triplicate ECGs may be performed as clinically indicated. The patient should be relaxed and in a recumbent or semi-recumbent position at least 5 minutes before recording an ECG. ECGs will be reviewed locally by the site and parameters will be entered into the EDC.

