##### 3.1.3 *Unscheduled Visits*

Unscheduled visits will not be included in by-visit summaries but will contribute to the derivation of best or worst-case values and will be presented in data listings. Visit windowing will not be used for handling unscheduled visits.

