### *3.8.2 Clinical Laboratory Tests*

Blood and urine samples for safety analysis of urinalysis, coagulation, chemistry, serology, endocrinology, and hematology parameters (see [Appendix B](#)) will be obtained as specified in the Schedule of Events in the protocol and processed using local laboratory. For purposes of analysis and reporting, laboratory values will be standardized using International System of Units (SI).

Pregnancy tests (serum or urine) will be performed at pre-specified timepoints.

Clinical laboratory evaluations will be summarized using descriptive statistics for continuous laboratory parameters (coagulation, chemistry, hematology, and endocrinology) for the values and changes from baseline at each scheduled visit. The minimum post-baseline value, maximum post-baseline value, and last post-baseline value will also be presented. Both scheduled and unscheduled post-baseline visits will be considered for the summaries of the last, maximum, and minimum post-baseline values.

Categorical serology and urinalysis parameters will be summarized using number and percentage of patients.

Abnormal laboratory results will be graded according to NCI-CTCAE version 5 as applicable. A shift table, presenting the 2-way frequency tabulation for baseline and the worst post-treatment grade according to the NCI-CTCAE grade will be provided for selected clinical laboratory tests when applicable. Both scheduled and unscheduled post-treatment visits will be considered in tabulation of the worst post-treatment grade.

The number and percentage of patients with laboratory abnormalities will be presented for applicable hematology and serum chemistry laboratory parameters.

Additionally, the number and percentage of patients with the following potentially clinically significant abnormal liver function test will be presented:

- ALT  $\geq 3 \times \text{ULN}$ ,  $\geq 5 \times \text{ULN}$ ,  $\geq 10 \times \text{ULN}$ , and  $\geq 20 \times \text{ULN}$
- AST  $\geq 3 \times \text{ULN}$ ,  $\geq 5 \times \text{ULN}$ ,  $\geq 10 \times \text{ULN}$ , and  $\geq 20 \times \text{ULN}$

- Total bilirubin  $\geq 2 \times \text{ULN}$
- Potential Hy's Law cases: ALT or AST  $> 3 \times \text{ULN}$ , total bilirubin  $\geq 2 \times \text{ULN}$ , and ALP  $< 2 \times \text{ULN}$  at the same visit

Clinical laboratory evaluations will also be listed by patient and abnormal values will be flagged.

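### QTcF threshold counts use scheduled visits only: they can miss a crossing seen on a clinically indicated ECG and never give the number of patients ever above a threshold

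*SAP*

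**What the plan says.** **QTcF.** SAP 3.8.4 says "patients experiencing QTcF elevation or change from baseline will be tabulated by scheduled visit for the following categories": above 450, 480 and 500 ms, and increases above 30 and 60 ms. No any-time or worst-value version of these categories is planned. The general rule in SAP 3.1.3 is "Unscheduled visits will not be included in by-visit summaries but will contribute to the derivation of best or worst-case values". Protocol 7.9 foresees ECGs outside the schedule: "Additional triplicate ECGs may be performed as clinically indicated".

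The same SAP section handles other ECG outputs differently. For the continuous summaries, "Both scheduled and unscheduled visits will be considered for summaries of the last and maximum post-treatment values". The shift table of overall ECG judgement uses scheduled and unscheduled visits, and "ECG assessments will be listed by patient".

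**Liver (secondary).** SAP 3.8.2 has a row that begins "Potential Hy's Law cases: ALT or AST". It requires ALT or AST above 3 x ULN, total bilirubin at or above 2 x ULN and ALP below 2 x ULN, all at one visit. Protocol 4.4 says "Patients who meet Hy's law will be discontinued from treatment". The note under Protocol Table 15 describes AST or ALT above 3 x ULN together with bilirubin above 2 x ULN, with no initial biliary obstruction and no other explanation. It does not say that the values must come from one visit.

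**The concern.** An ECG taken because something prompted it is more likely to be abnormal than a routine one. Under the two SAP rules read together, those ECGs are the ones left out of the threshold counts. A reader who sees zero in the row for QTcF above 500 ms would take it to mean that no patient exceeded 500 ms. The table supports only a narrower statement: none did at a scheduled visit.

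There is a second gap even if every ECG is on schedule. A by-visit table does not give the number of different patients who ever crossed a threshold, which is the usual way to state an outlier result. ECG change is part of a secondary endpoint in Part 1, and Part 1 is the only part that SAP section 5 leaves to be analysed.

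The liver row raises a lesser question of the same kind. A patient whose transaminase and bilirubin thresholds are crossed at different visits is not counted.

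**Working it through.** The plan states no figure to reproduce here. The check applies the written rules to invented patients and then sizes one missed case.

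**1. Scheduled-visit rule, one invented patient.** Scheduled QTcF 430 ms (taken as baseline) and 440 ms; unscheduled QTcF 505 ms.

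| Category | Scheduled ECGs | All ECGs |
|---|---|---|
| >450, >480, >500 ms | highest 440: in none | highest 505: in all three |
| Rise >30, >60 ms | 440 - 430 = 10: in neither | 505 - 430 = 75: in both |

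The patient is absent from all five categories as written and belongs to all five on an any-time count.

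**2. What by-visit counts can tell.** Let c_j be the number of patients in a category at scheduled visit j, and E the number ever in it on a scheduled ECG. Then max(c_j) <= E <= sum(c_j), with E also capped by the number of patients. If one patient is above 480 ms at each of two visits, the bounds are 1 <= E <= 2: it may be the same patient twice or two patients. Patients who crossed only at unscheduled visits come on top of E, and the table says nothing about them.

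**3. Size of one missed patient.** The documents give no QTcF event rate and the SAP does not state how many patients were treated. So I assume one missed patient and the maximum Part 1 size: 15 per arm, 30 overall. The exact (Clopper-Pearson) limits for x of n are: lower = 2.5% quantile of Beta(x, n-x+1), upper = 97.5% quantile of Beta(x+1, n-x). For x = 0 the lower limit is 0 and the upper is 1 - 0.025^(1/n).

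| n | Reported | With the patient counted |
|---|---|---|
| 30 | 0/30, 0% (0 to 11.6%) | 1/30, 3.3% (0.1 to 17.2%) |
| 15 | 0/15, 0% (0 to 21.8%) | 1/15, 6.7% (0.2 to 31.9%) |

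**4. Consistency within the SAP.** Unscheduled data enter the worst laboratory grade (3.8.2), the vital-sign minimum and maximum (3.8.3), the maximum QTcF and the ECG shift table (both 3.8.4). The closest parallel is Table 3-4, where patients are counted against blood-pressure and heart-rate limits using those minima and maxima. QTcF categories are handled differently, and no reason is given.

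**5. Same-visit liver rule, one invented patient.** First visit: ALT 6.0, bilirubin 1.2, ALP 1.0 x ULN. Second visit: ALT 2.8, bilirubin 2.5, ALP 1.1 x ULN. The first visit fails on bilirubin (1.2 < 2) and the second on ALT (2.8 is not > 3), so the same-visit count is 0. ALT exceeds 3 and bilirubin reaches 2 at some visit, so an any-time count is 1.

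**The case against.** **The data are not hidden.** Unscheduled ECGs reach the maximum and last QTcF summaries, the shift table and the listings, and with at most 30 patients a listing can be read line by line. This stands as far as visibility goes. It does not supply the count. The spread of maximum values can show that someone exceeded 500 ms, but not how many did. The shift table uses overall clinical judgement rather than QTcF limits, and a listing leaves the tally to the reader.

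**The stakes are small.** Summaries are descriptive, no decision uses these counts, the trial stopped after Part 1, and the Phase 1 table in Protocol Appendix F lists no QT or cardiac event among related events. All true. This limits the weight of the point but does not make the table complete.

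**The liver row is defensible.** A reader might infer that the one-visit condition contradicts the protocol. The documents do not support that. The Table 15 note and the coagulation footnote in Protocol Appendix B both describe the bilirubin rise as going along with the transaminase rise, and one visit is a fair way to put that into practice. The count is not limited to scheduled visits. All the tests sit in one chemistry panel and abnormal values are repeated often, which makes a same-visit capture more likely.

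**Nor can the liver row only undercount.** The SAP screen omits the protocol's exclusion of other causes, and its bilirubin limit includes exactly 2 x ULN where the protocol's does not. Patients with liver metastases may enter with AST or ALT up to 5 x ULN. So the row can also count patients whom the protocol's note would not.

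**Conclusion.** The QTcF point holds on the text. The category table can miss a patient whose only crossing was on an unscheduled ECG, and it does not give the number of patients ever above a threshold. It also departs from how the same SAP treats comparable extremes. One missed patient would be 3.3% of a full Part 1 or 6.7% of a full arm. That rests on an assumed single case and the maximum enrolment; it is not an estimated error.

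A reader might go further and infer that real cases have been dropped. The documents show no such case. They show only that the rule permits it, with the readings still visible elsewhere. No primary endpoint or decision rule is touched.

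The Hy's Law row is a secondary matter of sensitivity. It can miss a patient who crosses the limits at different visits, but it is neither a contradiction of the protocol nor an error in one direction only. The bilirubin limit (at or above 2 x ULN in the SAP, above 2 x ULN in the protocol) and the timing condition do differ in wording and should be reconciled.

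**What to change.** **Main change (SAP 3.8.4).** For each of the five QTcF categories, add a worst post-baseline row that uses scheduled and unscheduled ECGs, averages triplicates as already planned, and counts each patient once. Keep the by-visit rows. This follows the worst-case provision in SAP 3.1.3. The cost is one extra set of rows from data already collected. If the database is already locked, record the addition in the study report, as SAP section 1 requires for later deviations.

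**Optional (SAP 3.8.2).** Beside the same-visit row, add a supplementary row for patients with ALT or AST above 3 x ULN at any post-baseline draw and the bilirubin limit met at any post-baseline draw. Show dates and ALP values for review. The documents give no time window and no rule for ALP across visits, so I propose neither. The cost is a few more patients to review, some of whom will have another explanation. State in the SAP how its bilirubin limit and one-visit condition relate to the Table 15 note. These are counting definitions only and change nothing in patient management.

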### 3.8.5 *Physical Examinations*

Physical examinations will be performed as indicated in the Schedule of Events Schedule of Events in the protocol. All physical examination data will be listed by patient.

## 3.9 Quality of Life Evaluation

The quality-of-life evaluation is a secondary objective in both Part 2: Combination Dose Finding and Part 3: Combination Dose Expansion. Quality of Life (QoL) evaluations (EQ-5D-5L and QLQ-C30) are to be performed for clinical benefit assessment at baseline and every 12 weeks after Cycle 1 Day 1 in combination arms (Arms B and C).

### 3.9.1 *EQ-5D-5L*

The EQ-5D questionnaire consists of two parts: the EQ-5D descriptive and the EQ visual analogue scale (EQ VAS).

The EQ-5D descriptive comprises five dimensions: mobility, self-care, usual activities, pain/discomfort, and anxiety/depression. Each dimension has 5 levels: no problems, slight problems, moderate problems, severe problems, extreme problems (i.e., unable to walk for mobility). Each patient will self-rate his current state within each dimension.

The EQ VAS records the patient's self-rated health on a vertical visual analogue scale. The VAS varies from 0 "The worst health you can imagine" to 100 "The best health you can imagine". The VAS is used as a quantitative measurement of health outcome.

The number and percentage of patients with each level in each dimension will be presented. Changes from baseline of the VAS will be summarized descriptively.

### 3.9.2 EORTC QLQ-C30

EORTC QLQ-C30 (version 3.0) is a well-validated instrument that includes 30 items to assess health-related quality of life (HRQOL) in cancer patients. The first 28 questions use a 4-point scale (1=not at all to 4=very much) for evaluating five functional scales (physical, role, social, cognitive, emotional), three symptom scales (fatigue, nausea/vomiting, and pain) and other single item symptom measures. The last 2 questions use a 7-point scale (1=very poor to 7=excellent) to evaluate the global quality of life. Item scales used to compute scores from 0 to 100. For functional and global QoL scales, higher scores mean a better level of functioning; for symptom-oriented scales, a higher score means more severe symptoms.

If at least half of the items from a scale are answered, it is assumed that the missing items have values equal to the average of those items that are present for that respondent. Otherwise, the scale score will be set to missing.

EORTC QLQ-C30 scores and changes from baseline will be summarized descriptively. Negative change from baseline values indicated deterioration in health status or functioning and positive changes indicated improvement.

## 4 INTERIM ANALYSIS

In Arm B or C, an interim analysis of the primary outcome will be performed at the end of Stage 1 of the Combination Dose Expansion part of the study (once 12 evaluable patients have completed at least 1 disease evaluation or have discontinued from the study). Any treatment arm with an ORR <20% per RECIST (i.e., treatment arms with no more than 2 complete or partial responses) will be discontinued.

Available safety, efficacy, and PD data will be reviewed on an ongoing basis by the SRC.

## 5 CHANGES FROM PROTOCOL-SPECIFIED STATISTICAL ANALYSES

Considering the results of the part 1, with a total of 0 response observed from the 2 monotherapy arms the following analysis will not be performed:

- All analysis related to part 2 (combination dose finding) and part 3 (combination dose expansion) as trial stopped after part 1.
- iRECIST analysis in part 1 (monotherapy dose expansion): due to lack of repeated scans once PD by RECIST is assessed, most of the PDs by iRECIST remained unconfirmed and therefore survival endpoints per RECIST will not be analysed.

## 6 PROGRAMMING SPECIFICATIONS

Analyses will be performed using SAS® version 9.4 or higher. All available data will be presented in patient data listings sorted by patient and visit date as applicable. Detailed Programming Specifications will be provided in a separate document.

## 7 APPENDIX

## APPENDIX A: DATE IMPUTATION GUIDELINES

The following date imputation guidelines will apply to adverse events (Table 7-1**Error! Reference source not found.**), and for prior and concomitant medications (Table 7-2**Error! Reference source not found.**).

Table 7-1: Adverse Events date imputation guidelines

AE Start Date	AE Stop Date	Action
Known	Known/Partial/Missing	If start date < study drug start date, then not TEAE If start date ≥ study drug start date, then TEAE
Partial, but the known date components show that it cannot be on or after study drug start date	Known/Partial/Missing	Not TEAE
Partial, could be on or after study drug start date	Known	If stop date < study drug start date, then not TEAE If stop date ≥ study drug start date, then TEAE
	Partial	Impute stop date as latest date (i.e., last day of month if day is unknown or 31-Dec if day and month are unknown), then: If stop date < study drug start date, then not TEAE If stop date ≥ study drug start date, then TEAE
	Missing	Assumed TEAE
Missing	Known	If stop date < study drug start date, then not TEAE If stop date ≥ study drug start date, then TEAE
	Partial	Impute stop date as latest date (i.e., last day of month if day is unknown or 31st December if day and month are unknown), then: If stop date < study drug start date, then not TEAE If stop date ≥ study drug start date, then TEAE
	Missing	Assumed TEAE

Table 7-2: Prior and concomitant medication date imputation guidelines

CM Start Date	CM Stop Date	Action
Known	Known	If stop date < study drug start date, assign as PRIOR If stop date ≥ study drug start date, and start date ≤ end of treatment +90 days, assign as CONCOMITANT
	Partial	Impute stop date as latest date (i.e., last day of month if day unknown or 31-Dec if day and month are unknown), then: If stop date < study drug start date, assign as PRIOR If stop date ≥ study drug start date, and start date ≤ end of treatment +90 days, assign as CONCOMITANT
	Missing	If stop date is missing, then PRIOR will never be assumed or assigned If start date ≤ end of treatment, assign as CONCOMITANT
Partial	Known	Impute start date as earliest date (i.e., first day of month if day unknown or 01-Jan if day and month unknown), then: If stop date < study drug start date, assign as PRIOR If stop date ≥ study drug start date and start date ≤ end of treatment + 90 days, assign as CONCOMITANT
	Partial	Impute start date as earliest date (i.e., first day of month if day unknown or 01-Jan if day and month are unknown) and impute stop date as latest date (i.e., last day of month if day unknown or 31-Dec if day and month are unknown), then: If stop date < study drug start date, assign as PRIOR If stop date ≥ study drug start date and start date ≤ end of treatment + 90 days, assign as CONCOMITANT
	Missing	Impute start date as earliest date (i.e., first day of month if day unknown or 01 Jan if day and month unknown), then: If stop date is missing, then PRIOR will never be assumed or assigned If start date ≤ end of treatment + 90 days, assign as CONCOMITANT
Missing or Unknown	Known	If stop date < study drug start date, assign as PRIOR If stop date ≥ study drug start date, assign as CONCOMITANT
	Partial	Impute stop date as latest date (i.e., last day of month if day unknown or 31-Dec if day and month are unknown), then: If stop date < study drug start date, assign as PRIOR If stop date ≥ study drug start date, assign as CONCOMITANT
	Missing	Assign as CONCOMITANT

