##### 3.1.5 *Handling of Dropouts and Missing Data*

Unrecorded data values will be recorded as missing. Only recorded (i.e., complete) data values will be used for statistical analyses. In general, invalid, or missing values will not be imputed unless stated otherwise.

If needed, completely or partially missing start and end dates for medical history events, including date of initial diagnosis and last date of last progression for the primary cancer history, will be imputed in a conservative fashion as follows:

Date	Type of Missing Date	Handling of Missing Date
Event Start Date (e.g., YYYY-MM-DD)	Completely missing	No imputation will be applied.
	Only YYYY is available	Use the first day of YYYY to impute the missing month and date parts of the start date
	YYYY and MM are available, but DD is missing	Use the first day of MM to impute the missing date part of the start date
Event End Date (e.g., YYYY-MM-DD)	Completely missing	No imputation will be applied. The event will be considered ongoing at the end of study.
	Only YYYY is available	Use the last day of YYYY to impute the missing month and date parts of the end date
	YYYY and MM are available, but DD is missing	Use the last day of MM to impute the missing date part of the end date

For missing or partial AEs and concomitant medications dates, conservative conventions will be applied to assign the events to corresponding periods. AEs will be considered as treatment-emergent, and the medications will be considered as concomitant if the missing/partial dates cannot definitively exclude the treatment period. Handling incomplete dates (e.g., AE, and concomitant medications dates) are described in Table 7-1 and Table 7-2 from [Appendix A](#).

For patients lost to follow-up or with missing RECIST/iRECIST assessments, censoring rules for efficacy endpoints are defined in section 3.4.

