### *3.3.7 Prior and Concomitant Non-cancer Medications*

The used prior or concomitant non-cancer medications will be recorded in the electronic case report (eCRF) from 28 days prior to Cycle 1 Day 1 to the Safety Follow-Up Visit up to 90 days after last dose of study drug or the start date of a new cancer regimen, whichever is shorter.

Prior and Concomitant medications will be coded to anatomical therapeutic chemical (ATC) class and preferred term using the WHODrug Dictionary version Global B3, March 2022 or higher.

Numbers and percentages of patients taking prior and concomitant medications by ATC class and preferred term will be summarized for each arm by dose level in the Combination Dose Finding part of the study and by treatment arm in the Monotherapy Dose Expansion part and Combination Dose Expansion part and overall using descriptive statistics based on the Safety population.

All prior and concomitant non-cancer medication data will be listed by patient.

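### SAP Table 7-2 omits the 90-day extension for a known start and missing stop date, leaving some post-treatment medications with no class

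*SAP*

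**What the plan says.** SAP 3.3.7 opens the collection of prior and concomitant non-cancer medications 28 days before the first cycle begins. The window runs, by the shorter of two limits, "to the Safety Follow-Up Visit up to 90 days after last dose of study drug or the start date of a new cancer regimen". Protocol 5.5.3 sets the same window. SAP 3.3.7 then summarizes patients by ATC class and preferred term, and lists every medication by patient.

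Table 7-2 in SAP Appendix A assigns the class. It has nine combinations: start date known, partial or missing, by stop date known, partial or missing. Where start and stop are both known, the concomitant rule is "If stop date ≥ study drug start date, and start date ≤ end of treatment +90 days, assign as CONCOMITANT". Where the start is partial and the stop is missing, the start is imputed to the earliest possible date and the rule is "If start date ≤ end of treatment + 90 days, assign as CONCOMITANT". Where the start is known and the stop is missing, the rule is "If start date ≤ end of treatment, assign as CONCOMITANT". Both missing-stop rows with a known or partial start also state: "If stop date is missing, then PRIOR will never be assumed or assigned".

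SAP 3.1.5 gives the general principle for incomplete dates: "the medications will be considered as concomitant if the missing/partial dates cannot definitively exclude the treatment period".

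**The concern.** The known-start, missing-stop row is the only one of the six rows with a known or partial start whose limit stops at end of treatment. Because that row also bars the prior class, a record that fails its concomitant condition has nowhere to go. The table offers no third class and no default.

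The result runs against the completeness of the data. A record with an exact start date is left out, while the same record with only a month and year, or with no dates at all, is counted. What is at stake is the accuracy of one descriptive safety table, the summary of concomitant medications for Part 1. SAP Section 5 does not remove that table when it drops the analyses of Parts 2 and 3. A programmer who follows the row as written would have to leave these records unclassified or make up a rule.

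**Working it through.** There is no design figure to reproduce, because this is a date-classification rule. The check applies Table 7-2 to a medication whose true start is day d after end of treatment, with d from 1 to 90. Let S be the start date, E the stop date, F the first dose date and T end of treatment, so that S = T + d.

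| Start | Stop | Limit for concomitant | Start days 1 to 90 left unclassified |
|---|---|---|---|
| Known | Known | S ≤ T + 90 | 0 of 90 |
| Known | Partial | S ≤ T + 90 | 0 of 90 |
| **Known** | **Missing** | **S ≤ T** | **90 of 90** |
| Partial | Known | imputed S ≤ T + 90 | 0 of 90 |
| Partial | Partial | imputed S ≤ T + 90 | 0 of 90 |
| Partial | Missing | imputed S ≤ T + 90 | 0 of 90 |
| Missing | Known | none (E ≥ F is enough) | 0 of 90 |
| Missing | Partial | none (imputed E ≥ F is enough) | 0 of 90 |
| Missing | Missing | none (always concomitant) | 0 of 90 |

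The counts come from coding all nine combinations with assumed dates: first dose 1 June 2023, end of treatment 10 September 2023, and a stop 5 days after the start. They do not depend on those dates, for these reasons:

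1. Known start, stop known or partial. E ≥ S > T ≥ F, so the prior condition fails. S = T + d ≤ T + 90, so the record is concomitant.
2. Partial start. The imputed start is the earliest possible date and so cannot be later than the true start. It therefore also falls at or before T + 90.
3. Missing start. There is no upper limit on the start. Any stop after F, or a missing stop, gives concomitant.
4. Known start, missing stop. Prior is barred. Concomitant needs T + d ≤ T, which is false for every d ≥ 1. No class results.

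One example shows the effect. A drug started on day 30 after end of treatment and stopped on day 35 is concomitant. The same drug started on day 30 and still without a stop date has no class. If its start is recorded only by month, it is concomitant again.

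With 90 days added to the known-start, missing-stop row, its count goes from 90 of 90 to 0 of 90. The other eight rows are unchanged. For a start on or before end of treatment (d ≤ 0), the row already gives concomitant, before and after the change.

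**The case against.** The best defense is that the row may be deliberate. SAP 3.1.5 ties the concomitant class to the treatment period, and a known start after the last dose does exclude that period. The 90 days in SAP 3.3.7 are a collection window and not a definition of concomitant. Both observations are fair as far as they go. They do not explain the row, because the two rows with a known start and a known or partial stop count exactly the same post-treatment start dates as concomitant. A missing stop date cannot make a known start date fall further outside the treatment period. The SAP gives no reason for the difference.

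A second defense is that SAP Section 6 refers to separate programming specifications, so the produced table may be right. That is possible. The finding is about the rule the SAP states, and an unseen specification does not correct it.

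The arguments about size do stand:

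- A reader might infer that every ongoing medication begun in the 90 days after treatment is lost. Only those with a fully known start date are affected, and the window closes early if a new cancer treatment starts. The protocol's schedule also places the Safety Follow-Up Visit at no more than 90 days, so it may come sooner.
- A reader might infer that this is the usual form of record for drugs begun in follow-up, such as corticosteroids or hormone replacement for late immune-related events. Protocol 5.4.5.2 does say such events can appear months after the last dose. The documents do not say how ongoing medications are entered or how often stop dates are missing.
- The summary counts patients, so someone who took the same medication during treatment is already counted under it.

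**Conclusion.** The row is wrong as written: it contradicts the five comparable rows and leaves a defined set of collected records without a class. That set is non-cancer medications with a fully known start date after end of treatment, inside the collection window, and no stop date. They would be absent from the concomitant-medication summary by ATC class and preferred term.

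The consequence is small. The number of such records is not in the documents, and Part 1 was capped at 30 patients. The records remain in the listings, so no data are lost. Medication class does not enter ORR, DOR, PFS or OS: censoring for DOR and PFS turns on new anti-cancer treatment, whereas SAP 3.3.7 concerns non-cancer medications. A reader should not infer any effect on efficacy or on the decision to stop after Part 1.

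The conclusion assumes that end of treatment, which the SAP does not define, means the last dose of study drug. That is the natural reading given SAP 3.3.7. It also assumes that the table is applied literally.

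**What to change.** In Table 7-2, change the concomitant line of the known-start, missing-stop row to match the partial-start, missing-stop row: "If start date ≤ end of treatment + 90 days, assign as CONCOMITANT". Keep the line that bars the prior class. It would help to state in the same place that end of treatment means the date of the last dose.

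The cost is one phrase in the table and one line of code. If the SAP can no longer be revised because the database is locked, its Section 1 already provides for recording the departure in the Clinical Study Report. The concomitant-medication summary should then be checked for records that received no class.
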